6.2.2.1 Physical examination

The physical exam will document any baseline abnormalities as well as the baseline BMI, waist circumference and a seated blood pressure measurement.

6.2.2.2 Three Day Dietary Recall (Visit 1.1)

Data on recent dietary patterns will be collected for 7 days immediately prior to Visit 2. The participant will complete a diet diary during the week prior to Visit 2 that will be used to facilitate the dietary recall. Note that the last 24 hour recall for the day immediately prior to Visit 2 can be completed on the same day as Visit 2.

Three day dietary recalls will be performed by the CHPS bionutritionists. Dietary assessments are to be performed interactively using the Nutrition Data System program (University of Minnesota) that includes prompts for questions depending on the food item entered as part of the interview. Using this software, the diet information will be summarized according to the macronutrient composition (daily consumption of calories, protein, fat, carbohydrates and dietary fiber). Additionally, the data on fat and other macronutrients can be further subcategorized, such as according percent of calories from saturated, monounsaturated, and polyunsaturated fats.

6.2.2.3 Dietitian Evaluation

Caloric requirements will be estimated by the dietitian in the CHPS prior Visit 2 using standard methods to estimate metabolic requirements.³³ This will be completed prior to Visit 2 so that the CHPS metabolic kitchen can be prepared for the dietary needs of the participant prior to providing 3 days of outpatient emulsifier free food.. Participants who gain or lose weight will not have their food quantity adjusted to prevent further weight loss or gain as the effect of emulsifiers on body weight is one of the measures that the study will evaluate.

6.2.3 Post Screening Visit (Visit 2)

Post screening should be completed 4 days prior to admission to the CHPS.

6.2.3.1 Fitbit Distribution

Once participants are determined to be eligible, they will be given a Fitbit Flex to measure their activity level each day in the 4 days prior to admission. A study coordinator will set up the Fitbit Flex for the participant. The participants will be sent home with the Fitbit Flex and instructions on how to use, charge, and wear their Fitbit every day and through their return on the day of admission.

6.2.3.2 Sample Collection

Eligible participants will have blood, urine, and stool samples will be collected prior to beginning the emulsifier free diet. Blood and urine will be collected following an overnight fast (see section 6.1.1 and 6.1.2) at Visit 2. A stool sample will be collected by the participant at home either the day prior to Visit 2 or the morning of Visit 2. Participants will bring the stool sample to the visit. Study staff will provide the participant with collection materials and instructions for collecting the stool at home and returning it to study staff (See section 6.1.3).

6.2.3.3 Emulsifier Free Diet

Participants will be given food prepared by the CHPS kitchen. All participants will receive 3 full days' worth of freshly prepared emulsifier-free food at Visit 2. Participants will consume the emulsifier-free food exclusively for the three days prior to admission to CHPS. Other than the prepared study meals, participants may have water, coffee and tea with no added sugar or dairy as desired. No other food or drink is allowed.

6.2.3.4 Vital signs and Weight

Vital signs and weight will be recorded. Weight should be recorded with the participant wearing undergarments and a hospital gown prior to the first meal of the day. The patient should urinate prior to being weighed. Weight will be measured in triplicate. The participant should not be able to see the readout on the scale and should not be told their weight.

6.2.4 Day 1 of Inpatient Procedures (Visit 3.1)

All participants will arrive at the CHPS in the morning, having not eaten since 11:59PM the evening prior. All of the below procedures for day 1 will be the same for both study arms.

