4.4 Early Withdrawal of Participants

4.4.1 When and How to Withdraw Participants

Participants may be withdrawn from the study at any time if the investigator or the participant believes that the participant's safety will be jeopardized by continued participation, or if the participant does not follow study procedures. Likewise, participants will be withdrawn from the study if they withdraw consent.

5 Study Intervention

All foods will be prepared within the CHPS's metabolic kitchen without emulsifiers (unless specifically added). All participants will follow the same Western style diet (i.e. the only difference being portion size). The macronutrient percentages of calories for the study diet will be 55% carbohydrate, 30% fat, and 15% protein. The diet will be composed of two menus that will be consumed on alternating days. Water, coffee and tea will be provided as desired. Participants will have access to additional food outside of the meals provided, however, the entire serving of the previous meal must have been consumed. The additional food provided outside of the scheduled meals will consist of the food from the same Western style diet provided for each meal.

For the three days prior to admission, participants will be eating an emulsifier free diet at home. Food will be provided by the CHPS metabolic kitchen. After admission to CHPS, no emulsifiers will be consumed prior to dinner on Day 1. Thus, accounting for the 8 hours of nil per os status prior to admission, all participants will have approximately 80 hours of emulsifier free washout time prior to administration of the food containing CMC.

Participants will be randomly assigned to receive 0 or 15 gm per day of CMC (8 participants in each arm of the study). Beginning with the dinner meal on Day 1, all participants will consume one serving of brownie or sorbet (15 gm) per day that contain 0 or 2.5 gm CMC per serving. The brownie and sorbet servings will be provided at all three scheduled meals and scheduled snacks. Prior to eating any other food on the study menu, participants must consume the brownie and sorbet servings.

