6.1.7 Oral glucose tolerance test

On day 1 and 11, participants will complete a 2.5 hour oral glucose tolerance test. This test will be completed prior to breakfast following a 12 hour fast. At 08:00h, a catheter will be placed in an antecubital or forearm vein for blood sampling, with the arm placed in a heating pad to promote arterialization of venous blood. After 20 min of acclimatization to the catheter placement, baseline blood samples will be taken at -5 and -1 min prior to the ingestion of 75 grams anhydrous oral glucose over a 5 min period starting at $t = 0$ at ~08:30h. Subsequent blood samples will be collected at $t = 15, 30, 60, 90,$ and 120 min post-ingestion. All samples will be collected on ice into chilled EDTA tubes with protease inhibitor cocktail containing DPP4-inhibitor added immediately, centrifuged at 4 degrees C, aliquoted in ice, and stored at minus 80 degrees C until biochemical analysis. A total of 4 ml of blood will be collected at each

test. Glucose, free fatty acids, insulin, glucagon, and GLP-1/GIP will be the substances tested.

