6.2.4.11 Timing of meals

The first meal will be served following the oral glucose tolerance test or after the flexible sigmoidoscopy. All scheduled snacks and meals will be provided following the oral glucose tolerance test except during the flexible sigmoidoscopy. Lunch will be served at approximately 12:30h and dinner at approximately 18:00h. A snack will be provided at 15:00h and 21:00h. Beginning at the dinner meal, all participants will consume one serving of brownie or sorbet (15 gm) per day that contain 0 or 2.5 gm CMC per serving. Participants will be expected to finish each meal by the time of their next meal. There will be no limitation on the time to consume snacks. All food must be consumed by midnight.

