6.2.5.6 Timing of meals

Breakfast will be served at 09:00h. Lunch will be served at approximately 12:30h and dinner at approximately 18:00h. A snack will be provided at 10:30h, 15:00h and 21:00h on Days 2-9. Participants will be expected to consume snacks by the next meal with the last snack consumed by midnight on Days 2-9. On Day 10, the 21:00h intervention snack will be provided in addition to the intervention and meal at 18:00h. Participants will be expected to finish each meal by the time of their next meal or snack. Lunch should be finished within 30 minutes. On Day 10, all food must be consumed by 19:30h. No food or beverage other than water is to be consumed between midnight and breakfast on Days 2-9 and between 19:30h and breakfast on Day 10.

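### The protocol asks for a 12-hour fast before the Day 1 glucose tolerance test, but its only cutoff for that evening, 11:59PM, allows about 8.5 hours, against about 13 hours before Day 11

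*Combined protocol and SAP*

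**What the plan says.** Section 6.1.7 sets the method for the OGTT on Days 1 and 11: "This test will be completed prior to breakfast following a 12 hour fast". Sections 6.2.4.5 (Day 1) and 6.2.6.4 (Day 11) repeat the requirement. Section 6.1.7 also fixes the clock. The catheter goes in at 08:00, glucose is taken at about 08:30, and "baseline blood samples will be taken at -5 and -1 min prior to the ingestion of 75 grams anhydrous oral glucose".

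For the evening before Day 1, when participants are at home on take-home food, section 6.2.4 says: "All participants will arrive at the CHPS in the morning, having not eaten since 11:59PM the evening prior". Section 6.2.3.3, which governs the take-home diet, sets no evening limit and leaves water, coffee and tea unrestricted. In estimating the washout, section 5 reads: "accounting for the 8 hours of nil per os status prior to admission, all participants will have approximately 80 hours of emulsifier free washout".

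A midnight stop is the normal inpatient rule. For Day 1, section 6.2.4.11 says: "All food must be consumed by midnight". The evening before the Day 11 test is treated differently in section 6.2.5.6: "On Day 10, the 21:00h intervention snack will be provided in addition to the intervention and meal at 18:00h", and "On Day 10, all food must be consumed by 19:30h". The same section adds: "No food or beverage other than water is to be consumed between midnight and breakfast on Days 2-9 and between 19:30h and breakfast". The second of those intervals is the night before the Day 11 test.

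Section 7.2.3 compares glucose and insulin AUC between groups at Day 1, at Day 11 and as the change, using t-tests. It treats HOMA-IR and the 30-minute insulin-to-glucose ratio at the same time points. Serum hormones and cytokines, including insulin, leptin and ghrelin, get unpaired tests between groups or paired tests within groups.

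**The concern.** The two Day 1 rules classify the same person differently. Someone who eats at 23:00 complies with the arrival rule in section 6.2.4 and breaks the OGTT rule in section 6.2.4.5. Staff who check arrivals against section 6.2.4 would pass that person. The protocol asks for food intake to be recorded during the inpatient stay, but it does not ask for the time of last intake before the OGTT. A short fast on Day 1 might therefore go unnoticed and could not be allowed for later.

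The protocol deals with the same problem before Day 11 by moving the late snack forward and closing intake at 19:30. It has no counterpart for the evening before Day 1, which is the night staff cannot supervise. The two tests that form each change score may then start from different fasting conditions. At stake are the precision of the Day 1 and change-score metabolic measures, with 8 participants per arm, and the interpretation of any within-group change in fasting hormones.

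**Working it through.** **Inputs**
- Required fast: 12 h (sections 6.1.7, 6.2.4.5, 6.2.6.4).
- Glucose at about 08:30, so the first baseline draw is at about 08:25 (section 6.1.7).
- Latest permitted eating before Day 1: 23:59 (section 6.2.4).
- Latest permitted eating before Day 11: 19:30 (section 6.2.5.6).
- Nil-per-os time and washout: 8 h and about 80 h (section 5).

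**Step 1: latest stop that satisfies the 12-hour rule.** 08:30 − 12 h = 20:30. Eating between 20:30 and 23:59 is allowed by section 6.2.4 and ruled out by section 6.2.4.5.

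**Step 2: shortest fast each evening cutoff permits.** Fast = time of test − latest permitted intake.

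| Test | Cutoff | To first baseline draw | To glucose | Against 12 h, at glucose |
|---|---|---|---|---|
| Day 1 | 23:59 | 8 h 26 min | 8 h 31 min | 3 h 29 min short |
| Day 11 | 19:30 | 12 h 55 min | 13 h 00 min | 1 h over |

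The difference between the two guaranteed minimums is 13 h 00 min − 8 h 31 min = 4 h 29 min. The start time is itself approximate, so these are best read as about 8.5 h, 13 h and 4.5 h.

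**Step 3: does section 5 point to an earlier stop?** Three full days plus the stated nil-per-os time is 3 × 24 h + 8 h = 80 h, which reproduces the plan's figure. Eight hours before a morning arrival at about 08:00 fits a stop around midnight. This is only weak support, because the figure is a washout estimate and a loose one: counted to dinner on Day 1 at about 18:00, the total would be 72 h + 18 h = 90 h. It does show that section 5 gives no earlier cutoff. The midnight start for the urine sample in section 6.2.4.6 is not evidence either way, because section 6.2.6.5 uses the same phrase for Day 11, when the cutoff is 19:30.

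**Step 4: which analyses can be affected.** Let s be the average effect on a change score of a longer fast on Day 11 than on Day 1.
- *Between arms:* the evening before Day 1 comes before any CMC, and both arms follow the same rules, so s has the same expected value in each. The contrast contains s − s = 0. Variation in fast length from person to person can still add variance to Day 1 values and to changes.
- *Day 11 only:* untouched, because the 19:30 rule applies to everyone.
- *Within an arm:* a paired Day 1 to Day 11 difference keeps s, which cannot be separated from a real change over time.

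The documents give neither the actual fasting times nor the effect of fast length on these measures. No value can be put on s or on the added variance.

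**The case against.** The best reply is that the two rules are a looser and a stricter requirement and not a contradiction. Section 6.2.4 limits eating before arrival. Section 6.2.4.5, a little later under the same Day 1 heading, sets the specific condition for the OGTT. A participant who stops by 20:30 meets both, and staff who work from the OGTT section would ask for 12 hours. The consent form and any Visit 2 handout are not in the text and may give a time. All of this stands. It means 8.5 hours is the least the written cutoff permits, and not a description of what happened.

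It does not remove the point. The fast takes place at home, the only clock time the protocol states for that evening is 11:59PM, and the protocol itself found it necessary to write an explicit earlier cutoff before the Day 11 test.

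A second reply is that the consequence is small. Section 7.2.3 names only between-group tests for AUC, the 30-minute ratio and HOMA-IR, and a common shift cancels there. Aim 3 is worded as exploratory in section 2, and section 3.2 pre-specifies no efficacy or safety endpoints. This also stands, and it is why the severity is low. It does not cover the paired within-group tests of serum hormones in the same section, where a common shift would remain.

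**Conclusion.** The written cutoff for the evening before Day 1 does not deliver the 12-hour fast the protocol requires. It permits about 8.5 hours, and the minimum fasts before the two tests differ by about 4.5 hours. The possible consequences are extra noise in the Day 1 and change-score OGTT and HOMA-IR values, and a shift common to both arms in paired Day 1 to Day 11 comparisons of fasting insulin, leptin, ghrelin and similar measures. Section 7.2.3 does not name the time points for the paired tests, so the second consequence assumes that Day 1 and Day 11 are the pair.

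A reader might go further and infer that the Day 1 tests were done after short fasts, that the CMC effect on glucose handling is biased, or that a definite amount of power is lost. The documents support none of these. Anyone who follows the 12-hour rule fasts long enough, the rules are the same in both arms, and nothing in the text allows the noise to be sized. This is a low-severity clarification and not a threat to the trial's conclusions.

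**What to change.** In section 6.2.4, replace 11:59PM with a single cutoff of 19:30 on the evening before admission, with only water allowed afterwards, to match the Day 10 rule in section 6.2.5.6. A 19:30 stop gives about 13 hours before both tests. A 20:30 stop would leave 11 h 55 min at the first baseline draw and would not match Day 11.

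Give the instruction in writing with the food at Visit 2, and make clear that the coffee and tea allowance in section 6.2.3.3 ends at the same time. Bring the 8 hours in section 5 into line. Its 80-hour total need not change, because the earlier stop falls inside the third take-home day. Add a case report form field for the time of last intake before each OGTT, so that a short fast can be seen.

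The cost is an earlier evening cutoff for one night at home, one line of instruction, a few wording edits and one form field. No visit or sample is added.

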6.2.4.1 History and physical exam

Vital signs (blood pressure should be done sitting) and weight will be recorded. Weight should be recorded with the participant wearing undergarments and a hospital gown prior to the first meal of the day. The patient should urinate prior to be weighed. Weight will be measured in triplicate. The participant should not be able to see the readout on the scale and should not be told their weight.

A complete physical exam and medical history will be completed to assess for abnormalities present at baseline and to confirm absence of intercurrent illnesses that would make the participant ineligible. Because the participants may be anxious on the first day of the inpatient stay, we will not use blood pressure on Day 1 as an exclusion criteria as long as the blood pressure at screening met the inclusion criteria (section 4.2).

6.2.4.2 Adverse Events

Patients will be queried for adverse events.

6.2.4.3 Urine pregnancy Test

A urine pregnancy test will be repeated for all women.

6.2.4.4 Concomitant medications

Consumption of concomitant medications will be recorded in the study records. Participants will not be permitted to take any medications that are listed in the exclusion criteria during the study.

6.2.4.5 Oral Glucose Tolerance Test

Participants will complete a 2.5 hour oral glucose tolerance test. This test will be completed prior to breakfast following a 12 hour fast.

6.2.4.6 Sample collection

Blood, urine, and feces samples will be obtained. Up to 15 ml of urine samples will be collected prior to 09:00h after an overnight fast starting at midnight. Approximately 16cc of blood will be collected for metabolomics at each collection following an overnight fast prior to breakfast. Participants will be provided a stool collection kit to collect a stool sample on the day prior to admission or on the morning of admission. The first stool sample will be weighed, aliquoted and frozen. Participants will collect stool from all subsequent bowel movements. This stool will be weighed, the weight recorded and discarded. In addition, a stool sample will be collected by the participant at home either the day prior to Visit 3 or the morning of Visit 3. Participants will bring the stool sample to the visit. Study staff will provide the participant with collection materials and instructions for collecting the stool at home and returning it to study staff (See section 6.1.3).

6.2.4.7 Rectal Swabs

Prior to the flexible sigmoidoscopy, each participant will undergo a rectal swab. (See section 6.1.5).

6.2.4.8 Flexible Sigmoidoscopy

Following the oral glucose tolerance test, each participant will undergo a sigmoidoscopy to obtain biopsies from the area of approximately 15 cm from the anal verge.

6.2.4.9 Food Frequency Questionnaire

We will collect information on the participant's usual diet utilizing the Diet History Questionnaire II (DHQ II), a food frequency questionnaire (FFQ) developed by the Risk Factor Monitoring and Methods Branch (RFMMB) of the National Cancer Institute (NCI). The original DHQ I was designed based on cognitive research findings, to be easy to use. It had 124 food items and included both portion size and dietary supplement questions. The DHQ II has a food list that has been updated based on more recent dietary data and consists of 134 food items and 8 dietary supplement questions. There are four different versions of DHQ II. These four versions differ by time frame (the past year versus the past month) and whether or not questions are included about portion size. We will utilize the questionnaire that asks about the past month and includes questions about portion sizes for this study since we are interested in most recent intake.

6.2.4.10 Recording of diet

Participants will begin their randomized diets following the oral glucose tolerance test and flexible sigmoidoscopy at dinner. Participants will be instructed to consume only the food provided and no other food. Participants must eat all of the brownie and servings of sorbet provided. Participants will have access to additional food outside of the meals provided, however, the entire serving of the previous meal must have been consumed. The amount of food consumed will be recorded on the case report forms.

6.2.4.11 Timing of meals

The first meal will be served following the oral glucose tolerance test or after the flexible sigmoidoscopy. All scheduled snacks and meals will be provided following the oral glucose tolerance test except during the flexible sigmoidoscopy. Lunch will be served at approximately 12:30h and dinner at approximately 18:00h. A snack will be provided at 15:00h and 21:00h. Beginning at the dinner meal, all participants will consume one serving of brownie or sorbet (15 gm) per day that contain 0 or 2.5 gm CMC per serving. Participants will be expected to finish each meal by the time of their next meal. There will be no limitation on the time to consume snacks. All food must be consumed by midnight.

6.2.4.12 Activity Level Maintenance

Participants will be required to attain within 10% of the average number of daily steps that they took in the 3 days prior to admission. To achieve this, participants may be escorted on walks outside of the inpatient unit by a coordinator, as needed.

6.2.4.13 PROMIS Scale

Participants will complete the PROMIS scale prior to eating their first meal.

6.2.5 Day 2-10 of Inpatient Procedures (Visit 3.2-3.10)

All of the below procedures for day 2-10 will be the same for both study arms.

6.2.5.1 Vital Signs and Weight

Vital signs and weight will be recorded. Weight should be recorded with the participant wearing undergarments and a hospital gown prior to the first meal of the day. The patient should urinate prior to being weighed. Weight will be measured in triplicate. The participant should not be able to see the readout on the scale and should not be told their weight. The number of bowel movements during the prior day will also be recorded.

6.2.5.2 Adverse Events

Participants will be queried for adverse events.

6.2.5.3 Concomitant medications

Consumption of concomitant medications will be recorded in the study records. Participants will not be permitted to take any medications that are listed in the exclusion criteria during the study.

